Daily / Role Functioning	An7	I am able to do my usual activities	3 = Quite a bit 4 = Very Much
	An8	I need to sleep during the day	
	An12	I am too tired to eat	
	An14	I need help doing my usual activities	
	An15	I am frustrated by being too tired to	
		do the things I want to do	
Social Functioining	An16	I have to limit my social activity	-
		because I am tired	

FACIT-FATIGUE RESPONSE OPTIONS

All 13 items of the FACIT-Fatigue are measured on a Likert scale with 5 response options and range from 0 (Not at all) to 4 (Very Much).

FACIT-FATIGUE SCORING

To score the FACIT-Fatigue, reversals are first performed for the scores on two items (An5 and An7) then all individual items are summed to obtain a score. The sum of the item scores is multiplied by the number of items in the subscale, then divided by the number of items answered. This produces the final score which ranges from 0 to 52. Higher scores indicate less fatigue (Yellen et al.1997).

FACIT-FATIGUE RECALL PERIOD

The recall period of the FACIT-Fatigue is the past 7 days.

DATA

All data will stem from a single pivotal Phase III trial, REGENCY.

ANALYSES TO SUPPORT THE OBJECTIVE

RELIABILITY

Internal consistency - Internal consistency is an estimate of reliability based on the average correlation between items in a scale. This is represented by calculating Cronbach's alpha.

Calculate Cronbach's alpha using data from the 13 scale items in relation to the total FACIT-Fatigue scale score at Baseline. Cronbac's alpha ≥0.7 suggests reasonable internal consistency. In addition, estimates of lambda 2, 4, and omega will be calculated for comparison.

Test-retest reliability - Calculate two-way, mixed effects ICC between FACIT-Fatigue scores derived at Baseline and Week 24. Correlations ≥0.7 indicate reasonable test-retest reliability.

VALIDITY

Construct validity - assesses the degree to which a scale actually measures the construct it was designed to measure. Two estimates of construct validity will be used - convergent validity and discriminant validity.

Convergent validity - Tests if a scale is correlated with other scales that measure the same or related construct. Calculate Spearman's correlation coefficient and Weighted Kappa between:

- FACIT-Fatigue score and SF-36 Vitality, Physical Functioning, Bodily Pain, Role Physical, and General Health domain scores derived at Baseline
- FACIT-Fatigue score and SF-36 Physical Component Summary (PCS) score derived at Baseline

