Discriminant validity - Tests if a scale is independent from other scales that measure constructs that differ from the one being considered. Calculate Spearman's correlation coefficient and Weighted Kappa between:

- FACIT-Fatigue score and SF-36 Mental Health, Role Emotional, and Social Functioning domain scores derived at Baseline
- FACIT-Fatigue score and SF-36 Mental Component Summary (MCS) score derived at Baseline

Known groups validity - Tests if a scale can differentiate between groups known to differ in terms of a disease category. Patients will be grouped according to the British Isles of Lupus Assessment Group (BILAG) General domain and BILAG Musculoskeletal domain scores (A, B, or C/D/E). ANOVA will be used to test the mean differences in FACIT-Fatigue scores between groups. Effect sizes (mean difference/SD) will be calculated for the differences between adjacent groups. A second analysis will be conducted using patient groups based on differing scores for Safety of Estrogens in Lupus Erythematosus National Assessment-Systemic Lupus Erythematosus Disease Activity Index (SELENA-SLEDAI), a measure of reduction in global disease activity. Two groups will be formed: a high SELENA-SLEDAI score group (indicating more active disease - SELENA-SLEDAI score ≥10); and a low SELENA-SLEDAI score group (SELENA-SLEDAI <6). Both analyses will be based on Week 76 data.

Content Validity - This form of validity is typically established using qualitative interviews with patients, and sometimes physicians, to determine if a scale's content maps well with the patient's perspective of their disease burden. There is reasonable evidence for content validity in SLE/LN that will be culled from the existing literature.

RESPONSIVENESS OF FACIT-FATIGUE TO CHANGES IN DISEASE ACTIVITY

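### SAP Appendix 2 plans a weighted kappa between FACIT-Fatigue and SF-36 scores that share no categories; it should be dropped and Spearman's coefficient kept

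*SAP*

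**What the plan says.** SAP Appendix 2 sets out a psychometric validation of FACIT-Fatigue in lupus nephritis, intended to support possible label inclusion. On scoring it says: "This produces the final score which ranges from 0 to 52".

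Its definition of convergent validity is: "Tests if a scale is correlated with other scales that measure the same or related construct". It then plans Spearman's "correlation coefficient and Weighted Kappa between" the fatigue total and two kinds of comparator. One is the SF-36 physical summary score. The other is a set of five domains, listed as: "FACIT-Fatigue score and SF-36 Vitality, Physical Functioning, Bodily Pain, Role Physical, and General Health domain scores derived at Baseline".

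Its definition of discriminant validity is: "Tests if a scale is independent from other scales that measure constructs that differ from the one being considered". The same two statistics are planned there, against the SF-36 Mental Component Summary and for "FACIT-Fatigue score and SF-36 Mental Health, Role Emotional, and Social Functioning domain scores derived at Baseline".

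Neither section gives categories, cut points, a common metric, kappa weights, an expected size or a pass mark. The reliability section of the same appendix, by contrast, sets 0.7 for both Cronbach's alpha and test-retest reliability.

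Table 1 of the appendix files item An16, which begins "I have to limit my social activity", under social functioning.

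**The concern.** Convergent validity is defined in the appendix as a question about correlation. Weighted kappa answers another question: how closely two ratings agree when both use the same ordered categories. A fatigue total on 0 to 52 and an SF-36 domain or component score have no categories in common. Two programmers could therefore produce different kappas from the same data, and each would be following the SAP.

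On raw scores, or on cut points fixed in advance, kappa also falls when the scales differ in location or spread, however strongly the constructs are related. A discriminant scale could then show a higher kappa than a convergent one, the opposite of what the appendix sets out to show. What is at stake is the clarity of the validation evidence. Choosing the categories after seeing the data would look selective.

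**Working it through.** **The plan's own figure.** The SAP states no kappa, target correlation or threshold for these analyses, so there is nothing to reproduce. The stated score range does check: 13 items × maximum 4 = 52.

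**Inputs.** The documents give no SF-36 score metric, means, SDs or correlations with FACIT-Fatigue. All moments below are assumptions, written as mean/SD, and the raw-score quadratic form is one possible implementation that the SAP does not state.

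**Formula.** With quadratic weights on raw scores:

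- observed disagreement = s1² + s2² − 2·r·s1·s2 + (m1 − m2)²
- disagreement expected by chance = s1² + s2² + (m1 − m2)²
- kappa = 1 − observed/expected = 2·r·s1·s2 / [s1² + s2² + (m1 − m2)²]

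**Step 1: perfect association (r = 1), FACIT-F 33/11.**

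| Comparator | Calculation | Kappa |
|---|---|---|
| 50/20 | 440/(121 + 400 + 289) = 440/810 | 0.54 |
| 70/25 | 550/(121 + 625 + 1369) = 550/2115 | 0.26 |
| 40/20 | 440/(121 + 400 + 49) = 440/570 | 0.77 |
| 45/10 | 220/(121 + 100 + 144) = 220/365 | 0.60 |

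The association is the same in every row. Only location and spread change, and kappa runs from 0.26 to 0.77.

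**Step 2: reversal.** Against 70/25 with r = 0.8, kappa = 0.8 × 0.26 = 0.21. Against 40/20 with r = 0.6, kappa = 0.6 × 0.77 = 0.46. The weaker association gets the higher kappa.

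**Step 3: other FACIT-F moments.** The comparators assumed are General Health 40/20, Social Functioning 62/27, Mental Component Summary 43/11 and Physical Functioning 65/27.

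| FACIT-F | General Health, r = 0.50 | Social Functioning, r = 0.65 | Mental Component, r = 0.45 (discriminant) | Physical Functioning, r = 0.55 (convergent) |
|---|---|---|---|---|
| 30/11 | 0.35 | 0.21 | 0.26 | 0.16 |
| 35/11 | 0.40 | 0.24 | 0.36 | 0.19 |
| 40/9 | 0.37 | 0.24 | 0.42 | 0.19 |

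Both inversions appear in all three rows. In simulation (5,000 pairs per comparison) they also appear with linear weights; at 35/11 the four values are 0.23, 0.10, 0.18 and 0.07.

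**Step 4: fixed cut points.** Five equal-width bins (0 to 52 for FACIT-F, 0 to 100 for SF-36), quadratic weights, FACIT-F 35/11: Vitality (r = 0.75) gives 0.53, Social Functioning (r = 0.65) gives 0.57 and the Physical Component Summary (r = 0.60) gives 0.20. The order is again lost.

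**Step 5: each score cut at its own sample quartiles.** For r = 0.4, 0.5, 0.6, 0.7 and 0.8, quadratic kappa is 0.33, 0.43, 0.53, 0.63 and 0.72. It rises with r and ranks the associations as Spearman's coefficient does.

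**Step 6: the social item.** An16 is 1 of 13 items. In a one-factor simulation with an assumed item-specific overlap of 0.3 to 0.5 with SF-36 Social Functioning, omitting An16 lowers the correlation by about 0.02 to 0.05. For example, it falls from 0.616 to 0.576 at item loading 0.7 and overlap 0.5.

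**The case against.** The strongest reply is that the reversal belongs to an implementation the SAP never states. With matched quantile categories nothing is re-ordered, and pre-specifying such categories would also be a valid repair. That stands: the illustration shows what can happen under assumed moments, not what will. But in that case kappa adds nothing to the ordering Spearman gives, so there is still no reason to keep it.

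A second reply is that little turns on this. Spearman's coefficient is already planned for every pair, and no decision rule uses kappa. That also stands, and it limits the size of the point. A reader might infer that the FACIT-F key secondary result is weakened. The documents do not support this: that endpoint is tested by ANCOVA with multiple imputation (SAP 4.3.1.6), last in the testing order (SAP 2.1.1), and neither step draws on Appendix 2.

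A reader might also infer that listing SF-36 Social Functioning as a discriminant scale sets a valid instrument up to fail. The text does not go that far. The definition does speak of independence, but no threshold or pass/fail rule is attached to any validity coefficient, and the overlap is one item. Disqualifying the domain on Table 1's label would also call Role Emotional into question, since Table 1 appears to file several FACIT-Fatigue items under daily or role functioning. Where Social Functioning belongs is a judgement.

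**Conclusion.** The concern holds for the kappa. An agreement statistic is planned where the SAP's own definition asks about correlation, between scores with no shared categories, and without the choices needed to compute it. On raw scores or fixed cut points it can mislead about which association is stronger (0.21 at r = 0.8 against 0.46 at r = 0.6). On sample quartiles it is redundant. Those values rest on assumed means, SDs and correlations and, for the raw-score figures, on quadratic weights. The conclusion that the statistic is unspecified and unsuited to the question does not depend on them.

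The effect is confined to the psychometric appendix. No type I error rate, effect estimate or confirmatory test changes.

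On Social Functioning, only a note is warranted. Because Table 1 assigns An16 to that concept, a moderate correlation is to be expected and should not be read as failed discriminant validity.

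**What to change.** In SAP Appendix 2, delete weighted kappa from both the convergent and the discriminant validity sections, and report Spearman's coefficient with its 95% CI for each pair.

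As a minor addition, state in the discriminant section that a moderate correlation with SF-36 Social Functioning is expected because of An16. Moving that domain to the convergent list is optional.

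The cost is a wording change in an appendix and one statistic fewer to program. No new data are needed.

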Appendix 2 Psychometric Validation of the FACIT-Fatigue Scale in LN Patients: Analysis Plan

BACKGROUND

Patients with lupus nephritis (LN) experience significant symptoms due to their disease that impact their daily lives. Of the identified core symptoms of LN, fatigue is one of the most prevalent and bothersome to patients (Williams-Hall et al. 2022; Raymond et al. 2021; Eudy et al. 2022; Gallop et al. 2012; Mathias et al. 2018). In studies of patients with active proliferative LN, more than 90% of patients reported experiencing fatigue at a baseline evaluation (Daleboudt et al. 2011; Grootscholten et al. 2007; Arends et al. 2014). Furthermore, in these patients fatigue was generally reported as their most bothersome symptom. The frequency of fatigue has been shown to be similar between patients with and without active LN (Bland et al. 2018). Due to the importance of fatigue in the LN patient experience and the clinical and patient-reported significance of the symptom, it was deemed important to assess the effect of obinutuzumab on fatigue symptoms in LN in the Phase III REGENCY trial. In this study, fatigue was assessed using the FACIT-Fatigue scale. The associated key secondary endpoint is mean change from Baseline at Week 76.

This analysis plan has been developed to provide psychometric validation for the use of the FACIT-fatigue scale in LN patients in order to facilitate USPI inclusion.

OBJECTIVE

 To establish the reliability, validity, and responsiveness of the FACIT-Fatigue scale in LN patients to facilitate potential label inclusion..

The FACIT-Fatigue is presented in Table 1. The FACIT-Fatigue is one of many different FACIT scales that are part of a collection of health-related quality of life (HRQOL) questionnaires targeted to the management of chronic illness and referred to as The FACIT Measurement System (Webster et al. 2003). The FACIT-Fatigue is a 13-item measure that assesses self-reported fatigue and its impact upon daily activities and function (Tennant 2015).

Table 1 FACIT-Fatigue Scale (Version 4)

Health Concept	FACIT Item	Question	Response Options
Fatigue	HI7	I feel fatigued	0 = Not at all 1 = A little bit
	HI12	I feel weak all over	
	An1	I feel listless ("washed out")	
	An2	I feel tired	
Daily / Role Functioning	An3	I have trouble starting things because	
		I am tired	
	An4	I have trouble finishing things	
		because I am tired	
Physical Functioning	An5	I have energy	2 = Somewhat

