In this section, the responsiveness of the FACIT-Fatigue score in relation to changes in disease status is assessed. For this analysis, the extent to which important longitudinal changes in Physician's Global Assessment (PGA), Subject's Global Assessment (SGA), and BILAG grade are associated with changes in the FACIT-Fatigue score will be examined. PGA and SGA score changes will be classified as better, worse, or unchanged, with a 30% increase or decrease used as the criterion for classifying meaningful change. BILAG grade change between consecutive assessments will be categorized as more active, stable, or less active. Moving from a BILAG score of D/E to C or vice versa will be classified as stable since those changes are not considered clinically meaningful. ANOVA will be used to compare mean FACIT-Fatigue score change between groups. Both analyses will be based on Week 76 data.

DERIVATION OF MINIMUM CLINICALLY IMPORTANT DIFFERENCE (MCID) - A RESPONDER THRESHOLD FOR ASSESSING WITHIN-PATIENT IMPROVEMENT

In order to derive an MCID for the FACIT-Fatigue scale, the SF-36 Vitality Domain as an anchor will be employed. The Vitality domain has the advantage of assessing a similar construct to the FACIT-Fatigue scale and is built from fairly well-delineated categorical response choices ("all of the time"=1; 'most of the time"=2; "a good bit of the time"=3; "some of the time"=4; "a little of the time"=5; and "none of the time"=6). For this analysis, an SF-36 Vitality domain responder will be defined as a patient who satisfies the following:

How much of the time during the past 7 days...

VT1 - did you feel full of pep? (must score a 3 or less);

VT2 - did you have a lot of energy? (must score 3 or less);

VT3 - did you feel worn out? (must score 4 or higher);

VT4 - did you feel tired? (must score 4 or higher)

The mean improvement in FACIT-Fatigue score (rounded up to the nearest integer) for the subpopulation of SF-36 VT responders between Baseline and Week 76 will serve as the estimated MCID for the FACIT-Fatigue scale. The proportion of subjects from each treatment group who have improved by the MCID value or greater between Baseline and Week 76 will be calculated. A chi-square test will be conducted to evaluate the differences

REFERENCES

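### SAP Appendix 2 validates FACIT-Fatigue against BILAG and SELENA-SLEDAI, which the trial does not collect, and codes SF-36 Vitality for a form other than the one in use

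*SAP*

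**What the plan says.** Appendix 2 of the SAP sets out its purpose as "psychometric validation for the use of the FACIT-fatigue scale in LN patients in order to facilitate USPI inclusion". Its Data paragraph limits the source: "All data will stem from a single pivotal Phase III trial, REGENCY".

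Three parts of the appendix matter here.

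- **Known-groups validity.** The first analysis reads: "Patients will be grouped according to the British Isles of Lupus Assessment Group (BILAG) General domain and BILAG Musculoskeletal domain scores", with grades A, B and C/D/E compared by ANOVA. The second reads: "Two groups will be formed: a high SELENA-SLEDAI score group (indicating more active disease - SELENA-SLEDAI score ≥10"; the comparison group scores below 6. Both use Week 76 data.
- **Responsiveness.** Changes in PGA, SGA and BILAG are the three anchors. For the last, "BILAG grade change between consecutive assessments will be categorized as more active, stable, or less active".
- **MCID.** The anchor is a responder definition on the SF-36 Vitality domain. The SAP prints a six-level label-to-code map that includes "a good bit of the time'=3; 'some of the time'=4". The first item and its cut-off are given as "VT1 - did you feel full of pep? (must score a 3 or less"; the fourth as "VT4 - did you feel tired? (must score 4 or higher". The second item (energy) shares the first cut-off and the third (worn out) shares the fourth. The mean FACIT-Fatigue improvement among these responders becomes the MCID. The proportions reaching it are then compared between arms by chi-square.

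**The concern.** If Appendix 2 may use only this trial's data, every grouping variable and anchor has to be something the protocol collects. BILAG and SELENA-SLEDAI do not appear among its assessments, which would leave the known-groups section with nothing to analyse.

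The Vitality rule raises a separate problem. Its cut-offs are stated as numbers belonging to a six-level form. On a five-level form the same numbers can point to different answers, and an error in who counts as a responder would carry into the MCID and then into the between-arm comparison.

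At stake is the evidence intended to support a fatigue claim in the label. FACIT-F is a key secondary endpoint, placed last in the testing sequence of SAP Section 2.1.1.

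**Working it through.** The plan gives no figure to reproduce on this point. The check sets the appendix against the protocol's instrument list, schedules and SF-36 form, then enumerates the Vitality rule.

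**1. Is each variable collected?**

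Protocol Section 4.5.7 lists two clinician-reported instruments, PGA and SLEDAI-2K. The patient-reported list is FACIT-F, SF-36 v2 Acute, EQ-5D-5L and SGA. In protocol Appendix 1, the clinician-reported row names only PGA and SLEDAI-2K in Table 1 (through Week 76), Table 2 (later blinded treatment) and Table 3 (open-label treatment). The tests required for a suspected flare name the same two. In the protocol, BILAG occurs only in the abbreviation list and in the Section 3.3.1 description of an earlier rituximab cohort. SELENA-SLEDAI occurs nowhere outside SAP Appendix 2.

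| Appendix 2 use | Variable | Collected? |
|---|---|---|
| Known groups, analysis 1 | BILAG General grade | No |
| Known groups, analysis 1 | BILAG Musculoskeletal grade | No |
| Known groups, analysis 2 | SELENA-SLEDAI | No (SLEDAI-2K is) |
| Responsiveness | PGA | Yes |
| Responsiveness | SGA | Yes |
| Responsiveness | BILAG grade change | No |

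So 3 of 3 known-groups variables, and hence 2 of 2 analyses, are missing, as is 1 of 3 responsiveness anchors. These are complete lists and legible table rows, so lost or redacted text does not explain the absence.

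**2. Does the Vitality coding fit the form?**

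Item 9 of the form in protocol Appendix 11 has five labels with boxes numbered 1 to 5, and its first part asks about feeling *full of life*. The level *a good bit of the time* is not on it.

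| Collected label | SAP code | Form number | Energy items (pass if ≤3): SAP / form | Fatigue items (pass if ≥4): SAP / form |
|---|---|---|---|---|
| All | 1 | 1 | pass / pass | fail / fail |
| Most | 2 | 2 | pass / pass | fail / fail |
| Some | 4 | 3 | **fail / pass** | **pass / fail** |
| A little | 5 | 4 | fail / fail | pass / pass |
| None | 6 | 5 | fail / fail | pass / pass |

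Three of five labels carry different codes, but only *some of the time* crosses a cut-off. It does so on the 2 energy items and the 2 fatigue items, 4 of 4. Three of those items are legible in the extracted form; *worn out* is not, and is assumed to be present with the same five levels.

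**3. How far apart are the two readings?**

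Four items with five levels give 5⁴ = 625 answer patterns.

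- By the SAP's labels, two levels qualify on each energy item and three on each fatigue item: 2 × 2 × 3 × 3 = 36 patterns.
- By form number, three and two qualify: 3 × 3 × 2 × 2 = 36 patterns.
- Patterns in both: 2 × 2 × 2 × 2 = 16.
- Patterns classified differently: (36 − 16) + (36 − 16) = 40.

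The two rules admit equally many patterns but share fewer than half. These counts give each pattern equal weight; they are not expected proportions of patients.

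**The case against.** On the missing indices, the best defence is that SLEDAI-2K is plainly what was meant by SELENA-SLEDAI. It is collected at Week 76 and analysed under SAP Section 4.3.2.3, so the second known-groups analysis is easily rescued. That is fair as far as it goes, and it makes the SLEDAI gap smaller than the BILAG gap. But the SAP names SLEDAI-2K correctly elsewhere, while Appendix 2 spells out a different index with its own cut-offs of ≥10 and <6. Nothing in either document carries those cut-offs over to SLEDAI-2K, and the defence does nothing for BILAG.

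On the Vitality rule, the objection is stronger. The SAP prints its label-to-code map, and all five collected labels are on it. A programmer who follows the map reaches a single rule, with *some of the time* coded 4 on every item. The error arises only if the form's box numbers are used, and the documents do not say how responses are coded in the database. The form in the protocol is also marked as a sample. This point stands: the mismatch is a coding risk and not a certain error.

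It can also be said that restating the energy threshold on five levels is itself a choice, because people who would have answered *a good bit of the time* must now choose *most* or *some*. That is true and deserves a sentence of justification in the SAP.

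Finally, known-groups and responsiveness analyses compare disease-activity groups, not arms, so a deadline tied to unblinding matters most for the MCID chi-square, the only between-arm comparison in the appendix. That also stands, although fixing cut-offs in advance is good practice for the others.

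**Conclusion.** The concern holds. As written, Appendix 2 can produce no known-groups evidence and loses one of three responsiveness anchors. This rests on the protocol's instrument list and schedules being the full record of what is collected; nothing in either document suggests otherwise.

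The Vitality rule does not match the collected form. Read by label it gives one answer. Read by box number it reverses the classification of *some of the time* on every item, subject to the assumption about *worn out*. How many patients would be affected, and which way the MCID would move, cannot be worked out from the documents.

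The effect is confined to the supporting validation and the MCID responder comparison. The Week 76 FACIT-F ANCOVA (SAP Section 4.3.1.6), the testing sequence, type I error control and power do not depend on it. Reliability, convergent and discriminant validity, and responsiveness to PGA and SGA can still be run. It should be corrected, but it does not threaten the trial's main conclusions.

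**What to change.** Amend Appendix 2 before the sponsor is unblinded for the Week 76 analysis:

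1. Replace SELENA-SLEDAI with SLEDAI-2K at Week 76, and state and justify cut-offs for that index.
2. Remove BILAG from the known-groups and responsiveness sections, or replace it with a named measure that is collected. Keep PGA and SGA as responsiveness anchors.
3. Restate the Vitality responder rule by label, in the wording and five levels of the collected form: *all* or *most of the time* for *full of life* and *a lot of energy*; *some*, *a little* or *none of the time* for *worn out* and *tired*. Add a line explaining the energy threshold now that the intermediate level does not exist.

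The cost is SAP appendix wording. SLEDAI-2K, PGA, SGA and SF-36 v2 are already scheduled at baseline and Week 76, so no new data or visits are needed.

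### The FACIT-Fatigue MCID is anchored on a vitality state rather than on a change in vitality, so the derived value is not tied to improvement on the anchor and is not a minimal difference

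*SAP*

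**What the plan says.** The section of SAP Appendix 2 on deriving the MCID is headed "A RESPONDER THRESHOLD FOR ASSESSING WITHIN-PATIENT IMPROVEMENT". For this purpose "the SF-36 Vitality Domain as an anchor will be employed".

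The appendix states that "an SF-36 Vitality domain responder will be defined as a patient who satisfies the following", and what follows is a list of absolute levels on four items with a 7-day recall. The two positive items must be at level 3 or below, for example "VT2 - did you have a lot of energy? (must score 3 or less"). The two negative items must be at level 4 or above, for example "VT4 - did you feel tired? (must score 4 or higher"). In the appendix's coding, 1 is all of the time, 3 a good bit of the time and 4 some of the time.

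The MCID is then "The mean improvement in FACIT-Fatigue score (rounded up to the nearest integer) for the subpopulation of SF-36 VT responders between Baseline and Week 76". Its use is also specified: "The proportion of subjects from each treatment group who have improved by the MCID value or greater between Baseline and Week 76 will be calculated", followed by a chi-square test of the difference.

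In the responsiveness section just before, the appendix classifies other measures by change: "PGA and SGA score changes will be classified as better, worse, or unchanged", using a 30% criterion. BILAG is likewise categorised by change in grade. Those classifications serve the responsiveness analysis only.

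**The concern.** An anchor-based threshold for within-patient improvement needs an anchor that identifies patients who improved, and ideally those who improved by a small but noticeable amount. Here only the FACIT-Fatigue side is a change; the anchor side is a level. Two kinds of misclassification follow from the text:

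- A patient who met all four levels at baseline and still meets them counts as a responder, although no improvement in vitality was required.
- A patient who goes from tired all of the time (1) to tired a good bit of the time (3) has improved on that item but still fails the rule and is left out.

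The rule also sets no upper limit on improvement, so patients with very large gains enter the mean. Nothing in the procedure makes the result a minimum.

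What is at stake is the meaning of the MCID and of the per-arm proportions that reach it. The appendix says the validation work is meant to support inclusion in the US label, so the interpretation of this threshold matters.

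**Working it through.** The documents give no MCID value, no standard deviation and no baseline distribution of Vitality or FACIT-Fatigue, so there is no figure of the plan to reproduce. The check is a reading of the rule, followed by an illustration.

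**Reading the rule**

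1. Does any criterion refer to baseline, a change score or a transition? No. All four are levels.
2. Is a visit named for scoring the items? No. Week 76 is the natural reading, but it is not stated.
3. Can patients meet the rule at entry? Yes. Protocol Sections 4.1.1 and 4.1.2 set no minimum fatigue score. Appendix 2 cites studies in which more than 90% of patients with active proliferative LN reported fatigue at baseline, but being tired or worn out some of the time (4) passes the negative items. That figure makes baseline responders less likely without excluding them.
4. Does another section of the protocol or SAP add the missing condition? No.

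**Illustration on assumed values**

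Let s be the share of Vitality responders who already met the rule at baseline, d_new the mean FACIT-Fatigue change in those who newly met it, and d_well the mean change in those already in the state. The SAP's estimator is then

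MCID = (1 − s) × d_new + s × d_well, rounded up.

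With d_new = 10 and d_well = 1 (both assumed):

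| s | Mean | Rounded up |
|---|---|---|
| 0% | 10.0 | 10 |
| 20% | 8.0 + 0.2 = 8.2 | 9 |
| 40% | 6.0 + 0.4 = 6.4 | 7 |
| 60% | 4.0 + 0.6 = 4.6 | 5 |

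The result stays at 10 while 10 − 9s exceeds 9, that is, for any s below 1/9 (about 11%).

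Other assumed inputs, with d_well between 0 and 2:

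- d_new = 6: the value is 6 at s = 0%. At s = 60% it is 3 (0.4 × 6 + 0 = 2.4) to 4 (0.4 × 6 + 0.6 × 2 = 3.6).
- d_new = 12: the value is 12 at s = 0%. At s = 60% it is 5 (0.4 × 12 + 0 = 4.8) to 6 (0.4 × 12 + 0.6 × 2 = 6.0).

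**Direction**

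Suppose a share g of the new responders are large improvers (mean d_large) and the rest improve minimally (mean d_min). Then d_new = (1 − g) × d_min + g × d_large, and before rounding

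MCID − d_min = (1 − s) × g × (d_large − d_min) − s × (d_min − d_well).

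The first term pushes the value above a minimal difference. The second pulls it below whenever d_well is less than d_min. The documents fix none of these quantities, so the sign of the error is unknown.

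**The case against.** **New responders may be meant.** The heading speaks of within-patient improvement, and the estimator's wording could be read as response attained between Baseline and Week 76. The listed criteria contain no such condition, and the interval reads more naturally as the period of the FACIT-Fatigue change. Even if new responders were intended, the text has to say so, and the mean would still include large improvers.

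**The size is assumed.** This stands. The 10-point and 1-point changes and every share are assumptions. The cited high prevalence of baseline fatigue, and the need to meet all four items together, give no support to shares of 40% to 60%. A patient who passes while tired some of the time could also still improve, so a near-zero change in already-well patients is not certain.

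**Stronger readings a reader might infer, which the documents do not support:**

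- *That the threshold does not measure within-patient improvement at all.* The FACIT-Fatigue side is a within-patient change from Baseline to Week 76. What is missing is the link to improvement on the anchor.
- *That the arm comparison has no valid threshold or is biased.* One cut-off, derived without reference to arm, is applied to both randomised arms. It does not by itself favour either arm. The weakness lies in calling the cut-off a minimum important difference.
- *That a key secondary result is at risk.* SAP Section 4.3.1.6 analyses change in FACIT-F by ANCOVA and does not use the MCID. The hierarchy in SAP Section 2.1.1 tests that change, and an MCID-responder proportion is not among the endpoints listed in SAP Section 1.1.1.

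**Conclusion.** The point holds as a matter of definition: as written, the anchor is a state with no baseline condition and no named visit. The derived value is therefore neither tied to improvement in vitality nor limited to minimal improvers, and it depends on how many patients were already well at entry.

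How far it would be off, and in which direction, cannot be determined from the documents. The illustrated range of 10 down to 5 rests wholly on assumed inputs, and it shows only the downward pull from already-well patients.

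The effect is confined to interpretation of the MCID, of the proportions reaching it, and of the associated chi-square test. The change should be made because of the intended labelling use, but no confirmatory conclusion of the trial turns on it.

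**What to change.** Before unblinding, amend SAP Appendix 2 as follows:

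1. Define the anchor by change in the SF-36 v2 Vitality score from Baseline to Week 76, in pre-specified categories: worse, unchanged, minimally improved, much improved. The documents supply no cut-offs for these, so the sponsor must choose and justify them.
2. Take the MCID from the minimally improved category.
3. Report mean FACIT-Fatigue change in every category, including unchanged, so that a reader can see whether the threshold separates improvement from no change.

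If the state-based rule is kept, say that it is scored at Week 76, require that it was not met at baseline, and do not call the resulting mean a minimum important difference. Excluding baseline responders alone is not enough, because the mean would still run over everyone who newly reached the state, however large the gain.

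The cost is appendix wording and a smaller anchor group, hence a less precise estimate. No new data are needed: Protocol Appendix 1, Table 1 already schedules SF-36 v2 at baseline and at Weeks 24, 50 and 76.

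While the section is open, the item coding should also be reconciled with the form. Appendix 2 uses six response levels, whereas the SF-36 form in Protocol Appendix 11 shows five. That is a separate matter; the present point holds under either coding.
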